2. LIST OF ABBREVIATIONS

Term	Definition / description
ADR	Adverse drug reaction
AE	Adverse event
AF	Atrial fibrillation
ASA	Acetylsalicylic acid
BI	Boehringer Ingelheim
CHADS ₂	Congestive heart failure, hypertension, age ≥ 75 , diabetes, prior stroke/transient ischemic attack
CHA ₂ DS ₂ -VAS _C	Risk factor for stroke and thrombo-embolism in non-valvular AF expressed as a point based scoring system
CI	Confidence interval
CrCl	Creatinine clearance
CRF	Case Report Form
CT	Clinical trial
CTR	Clinical Trial Report
DE	Dabigatran
EEA	European Economic Area
ECG	Electrocardiogram
EDC	Electronic Data Capture
EU	European Union
GFR	Glomerular Filtration Rate
HAS-BLED	Risk score for bleeding: Hypertension, abnormal renal function, prior stroke, prior bleeding, labile INR, age >65 , drugs or alcohol
IA	Interim analysis
ICH	International Conference on Harmonisation
INR	International Normalized Ratio
ISPE	International Society for Pharmacoepidemiology
ITT	Intention to treat
KM	Kaplan Meier
MBE	Major Bleeding Event
MedDRA	Medical Dictionary for Drug Regulatory Activities
MI	Myocardial Infarction
MDRD	Modification of diet in renal disease
NOAC	New oral coagulant/Non-VKA oral coagulant

Term	Definition / description
NSAID	Non-steroidal anti-inflammatory drugs
OAC	Oral Coagulant
OC	Operations Committee
PAD	Peripheral Artery Disease
PGP	P-glycoprotein
PS	Propensity Score
PV	Protocol violation
Q1	Lower quartile
Q3	Upper quartile
QD	Once a day /lat. quaque die
SAE	Serious Adverse Event
SEE	Systemic Embolism
SD	Standard deviation
SEAP	Statistical and epidemiological analysis plan
SPAF	Stroke Prevention in Atrial Fibrillation
CTL	Clinical Trial Leader
TIA	Transient ischemic attack
US	United States (of America)
VKA	Vitamin K antagonist
WHO	World Health Organization

3. INTRODUCTION

As per ICH E9 [1] and the ISPE Guidelines of Good Pharmacoepidemiology Practice [2], the purpose of this document is to provide a more technical and detailed elaboration of the principal features of the analyses described in the protocol, and to include procedures for executing the statistical analyses of the data. This document describes the interim and final analyses of Phase III for the global study 1160.129 as well as for the study 1160.136 (EU/EEA incl. Switzerland). The interim and final analyses of phase II are described in a separate document. In addition, the propensity score analyses to assess comparability that are performed during the course of the study are also described in a separate analysis plan.

If not specified differently, all of the described analyses in this document are to be done for 1160.129 as well as for 1160.136.

This SEAP assumes familiarity with the registry protocols including Protocol Amendments. In particular, the SEAP is based on the planned analysis specification as written in the registry protocol Section 7 “Statistical Methods and Determination of Sample Size”. Therefore, SEAP readers may consult the registry protocols for more background information on the study, e.g., on study objectives, study design and population, treatments, definition of measurements and variables, planning of sample size.

SAS® Version 9.4 or later will be used for all analyses.

4. CHANGES IN THE PLANNED ANALYSIS OF THE STUDY

Patients that did not take the initially prescribed medication (defined as: not taken one single dose of prescribed medication) do not provide any information on safety and effectiveness of the antithrombotic therapies and will therefore be excluded from all main outcome analyses.

The 1160.129 protocol specifies that 6,000 patients are required in the VKA and DE groups for the comparative analysis. However due to the lower than expected uptake of DE, this number cannot be reached. Acknowledging the smaller precision expected as a consequence of the reduced sample size and the potential limitations, the comparative analysis will still be conducted.

The sensitivity analysis, “a weighted, multivariate regression analysis based on the incomplete failure time data for the individual components of” the composite outcome that was specified in the 1160.129 protocol as an optional analysis will not be implemented.

5. OUTCOMES

5.1 MAIN OUTCOMES

The objectives of the study are

a) To investigate the patient characteristics influencing the choice of antithrombotic treatment for the prevention of stroke in non-valvular atrial fibrillation (AF) patients.

In order to address objective a), the same variables (demographic and lifestyle factors, disease characteristics, antithrombotic treatment characteristics and other chronic concomitant medication) will be defined and classified as for the Phase II interim study report for 1160.129 (c02207362-02) [\[3\]](#). Antithrombotic treatment groups are defined in [Section 6.1](#).

b) To collect real world data on important outcome events of antithrombotic treatments for the prevention of stroke.

The following events were considered in the 1160.129 protocol as “important outcome events”:

- Stroke (hemorrhagic and ischemic, uncertain classification)
- Transient ischemic attack (TIA)
- Systemic embolism (SEE)
- Pulmonary embolism
- Myocardial infarction (MI)
- Major bleeding events (including life-threatening bleeding events; see definition in study protocol) (MBE)
- Life-threatening bleeding events (see definition in study protocol; derived from bleeding page except for fatal bleeds which are derived as all MBEs which are linked to an SAE with “outcome= fatal” and/or “seriousness code=fatal”).
- All cause death
- Vascular death

In addition, the following two composite outcomes, also defined in the 1160.129 protocol, will be analyzed:

- Stroke, systemic embolism, myocardial infarction, life-threatening bleeding events and vascular death
- Stroke, systemic embolism, myocardial infarction and vascular death (vascular composite outcome)

The outcome event analysis will primarily be based on the data collected on the outcome CRFs (event (yes/no) and date of occurrence). The only exceptions will be made for patients who died, i.e. patients with:

- fatal AEs and without the death being documented on the outcome CRF; the death will be considered in the outcome analysis with “date of death= end date of AE”.
- “vital status=dead” and without the death being documented on the outcome CRF or on an AE form; the date of death from the vital status page will be used.

During the data cleaning process, adverse events potentially indicating an outcome event with no matching entry on the outcome CRFs will be queried.

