In a real-world setting, VKA treatment often results in INR values outside of the target therapeutic range ([R10-0768](#), [R09-1522](#)), leaving patients at increased risk of stroke or bleeding. To address the many short comings of VKAs, multiple new oral anticoagulants are in clinical development including mainly direct thrombin inhibitors and factor Xa inhibitors ([P07-08370](#)). Dabigatran, a direct thrombin inhibitor, has been approved for the prevention of stroke and systemic emboli in patients with AF in many countries worldwide, including the United States, Canada, Japan, Australia, Korea, Mexico, Brazil, as well as EU. In the RE-LY trial, an 18,113 randomized clinical patient study ([P09-11669](#)) dabigatran (150 mg b.i.d.) has been shown to significantly reduce the occurrence of stroke (both ischemic and hemorrhagic) and systemic emboli compared to warfarin while having a comparable rate of major bleeding. In the same trial dabigatran (110 mg b.i.d.) was demonstrated to be non-inferior to warfarin for the prevention of stroke and systemic emboli while resulting in statistically significant fewer major bleeds in the same study. Importantly, both doses of dabigatran reduced the occurrence of intracranial hemorrhage in a statistically significant manner compared to warfarin ([P09-11669](#)). Of note, dabigatran has been taken up as adequate treatment alternative to VKAs in major treatment guidelines (e.g. USA, Canada, EU) during recent revisions ([P11-00444](#), [P10-14910](#), [P10-10141](#), [P10-14358](#))

With the approval of novel anticoagulants for stroke prevention in patients with AF, changes in antithrombotic treatment patterns will occur. The GLORIA-AF Registry Program is designed to collect real-world data to assess these changes.

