© 2014 Boehringer Ingelheim International GmbH or one or more of its affiliated companies. All rights reserved.

This document may not - in full or in part - be passed on, reproduced, published or otherwise used without prior written permission.

The following definitions apply and should be used as a guide when reporting a thrombotic event:

Stroke:

Stroke is an acute onset of a focal neurological deficit of presumed vascular origin lasting for 24 hours or more or resulting in death. The stroke is categorized as ischemic or hemorrhagic or uncertain classification (based on CT or MR scanning or autopsy). Fatal stroke is defined as death from any cause within 30 days of stroke. Severity of stroke will be assessed by modified Rankin scale (see [Table 10.1:4](#)) at discharge from hospital and/or at 3-6 months later (if available).

Transient ischemic attack (TIA):

TIA is defined as a transient episode of neurological dysfunction caused by focal brain, spinal cord, or retinal ischemia without acute infarction ([P11-00444](#)).

Systemic embolism:

Systemic embolism is an acute vascular occlusion of the extremities or any organ (kidneys, mesenteric arteries, spleen, retina or grafts), typically documented by angiography, surgery, scintigraphy, or autopsy.

Pulmonary embolism:

- A patient has to fulfil the following criteria:
 1. Typical symptoms or signs (e.g., dyspnoea, left or right sided chest pain worsening on respiration, etc.) suggestive of pulmonary embolism

AND at least one of the following two criteria:

2. CT pulmonary angiography demonstrating an intraluminal filling defect in segmental or more proximally located pulmonary arteries
 3. High probability ventilation - perfusion lung scan, i.e. at least segmental perfusion defect at perfusion scan with normal ventilation at ventilation scan
- The definition of pulmonary embolism is also met if a patient fulfils at least criteria 2) or 3) above.

Myocardial infarction:

- In patients **not** undergoing PCI or CABG: A patient has to fulfil either the criteria:
 - Development of significant Q-waves in at least 2 adjacent ECG leads.

Or at least 2 of the following three criteria:

Proprietary confidential information.

© 2014 Boehringer Ingelheim International GmbH or one or more of its affiliated companies. All rights reserved.

This document may not - in full or in part - be passed on, reproduced, published or otherwise used without prior written permission.

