- Typical prolonged severe chest pain of at least 30 min
 - ECG changes suggestive of myocardial infarction including ST-changes of T-wave inversion in the ECG).
 - Elevation of troponin or CK-MB¹ to more than upper level of normal (ULN) or, if CK-MB was elevated at baseline, re-elevation to more than 50% increase above the previous level.
- After PCI (within 24 h)
Elevation of troponin or CK-MB¹ to more than 3xULN or, if CK-MB is elevated at baseline, re-elevation to more than 3xULN and a more than 50% increase above the previous level, and/or development of significant Q-waves² in at least two adjacent ECG leads.
 - After coronary artery bypass grafting (within 72 h)
Elevation of CK-MB¹ to more than 5xULN or, if CK-MB was elevated at baseline, re-elevation to more than 5xULN and a more than 50% increase above the previous level, and/or development of significant Q-waves² in at least two adjacent ECG leads.

¹Total CK if CK-MB was not available ²A new Q-wave with a duration of at least 0.04 seconds and a depth of more than a quarter of the amplitude of the corresponding R-wave, in at least 2 adjacent leads

Major bleeding, defined as meeting one or more of the following criteria ([R11-1250](#), [P11-05406](#)):

- Overt bleeding associated with a reduction in haemoglobin of at least 20 grams per liter or leading to a transfusion of at least 2 units of blood or packed cells
- Symptomatic bleeding in a critical area or organ: Intraocular, intracranial, intraspinal or intramuscular with compartment syndrome, retroperitoneal bleeding, intra-articular bleeding or pericardial bleeding
- Life-threatening bleeding

Life-threatening bleeding, defined as meeting one or more of the following criteria:

- Symptomatic intracranial bleed
- Reduction in haemoglobin of at least 50 grams per liter
- Transfusion of at least 4 units of blood or packed cells, associated with hypotension requiring the use of intravenous inotropic agents
- Necessitated surgical intervention
- Fatal bleeding

Deaths

Deaths will be classified as being: vascular (including bleeding); non-vascular, due to other specified causes (e.g., malignancy), or unknown cause, when cause is not known.

Proprietary confidential information.

© 2014 Boehringer Ingelheim International GmbH or one or more of its affiliated companies. All rights reserved.

This document may not - in full or in part - be passed on, reproduced, published or otherwise used without prior written permission.

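### SAP 5.1 has no rule that counts a haemorrhagic stroke as a life-threatening or major bleed, so one recorded only as a stroke may be left out of the bleeding analyses

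*SAP*

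**What the plan says.** **Protocol 5.1.2.** The criteria for life-threatening bleeding include "Symptomatic intracranial bleed" and "Fatal bleeding", and each is sufficient alone. Life-threatening bleeding is in turn one of the criteria for major bleeding, and symptomatic intracranial bleeding is also listed directly under major bleeding as a critical site. Stroke is a separate outcome: "The stroke is categorized as ischemic or hemorrhagic or uncertain classification", based on imaging or autopsy.

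**SAP 5.1, general source.** "The outcome event analysis will primarily be based on the data collected on the outcome CRFs (event (yes/no) and date of occurrence"). The only exceptions concern patients who died. SAP 6.8 says the same: outcome event pages, plus deaths from the vital status or SAE page.

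**SAP 5.1, bleeding outcomes.** The MBE bullet reads "Major bleeding events (including life-threatening bleeding events; see definition in study protocol) (MBE") and names no page. The life-threatening bullet also cites the protocol definition, then adds a source: "derived from bleeding page except for fatal bleeds which are derived as all MBEs which are linked to an SAE with" a fatal outcome or seriousness code.

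**SAP 5.1, data cleaning.** "adverse events potentially indicating an outcome event with no matching entry on the outcome CRFs will be queried".

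**SAP 7.6.** Incidence rates and cumulative risks are planned for all important outcome events, which include MBE and life-threatening bleeds. Major bleeding has its own dabigatran-VKA Cox model, subject to enough events. Haemorrhagic stroke is analysed separately as a further outcome.

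**The concern.** A haemorrhagic stroke is an intracranial bleed with symptoms, so under the protocol it belongs to three outcomes: stroke, life-threatening bleed and MBE. The SAP gives life-threatening bleeds one source, the bleeding page, with an exception for fatal bleeds only. Whether a haemorrhagic stroke reaches the bleeding outcomes then depends on the site making a second entry for the same event.

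These are among the most severe bleeds, and a loss need not be equal between groups. In its summary of RE-LY, Protocol 1.1 states that "both doses of dabigatran reduced the occurrence of intracranial hemorrhage in a statistically significant manner compared to warfarin". If some haemorrhagic strokes are recorded only as strokes, more events would probably be lost under VKA than under dabigatran. The life-threatening bleed rates, and possibly the MBE rates and Cox model, would then be too low by different amounts in the two groups.

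The fatal-bleed rule raises a second, conditional question. It looks for fatal bleeds among events that are already MBEs, whereas under the protocol being fatal is enough to make a bleed an MBE.

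**Working it through.** The plan states no figure for this point. The check compares texts, followed by an illustration of size.

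**1. Is a haemorrhagic stroke a bleed by definition?** Protocol 5.1.2 requires a focal deficit lasting at least 24 hours or ending in death, so the event is symptomatic; if haemorrhagic, it is intracranial. It meets the life-threatening criterion and so the MBE criterion.

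**2. Does any SAP rule put it there?**
- SAP 5.1, life-threatening bleeds: bleeding page, exception for fatal bleeds only. No.
- SAP 5.1, MBE: protocol definition, no page named, no mention of stroke. Not stated.
- SAP 6.8: outcome event pages plus deaths. No.
- SAP 7.6, further outcome events: haemorrhagic stroke is analysed in its own right and not added to bleeding. No.

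**3. Would cleaning catch it?** The query concerns adverse events without a matching outcome entry. An intracranial haemorrhage SAE may be matched to the stroke entry. The SAP does not say whether matching is by outcome type, and it states no stroke-against-bleeding check.

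**4. Fatal bleeds.** There are two readings of how MBE status is set.
- The site answers yes or no under the protocol definition: a fatal bleed is recorded as an MBE, and the SAE link only labels it fatal. Nothing is lost.
- MBE is programmed from the non-fatal criteria: a fatal bleed outside the listed sites, with no qualifying haemoglobin fall, transfusion or surgery, is not an MBE and so is never selected.

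The SAP does not say which reading applies.

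**5. Composite outcomes.** Both contain stroke and vascular death, and Protocol 5.1.2 classes bleeding deaths as vascular. These patients still count there.

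**6. How many events are at issue?** Protocol 7.6 gives about 4,019 patient-years for a Phase III cohort of 2,000 with 25% yearly loss over three years. This reproduces: 2,000 × (1 − 0.75³) / (−ln 0.75) = 4,019.2. At the protocol's expected 1 to 3 MBE per 100 patient-years, this is 40 to 121 MBEs per cohort. The documents do not give the share of MBEs that might go unrecorded as bleeds, so it is assumed:

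| Assumed share lost | Events lost (of 40 to 121) | A rate of 2.0 would read |
|---|---|---|
| 0% | 0 | 2.0 |
| 5% | 2 to 6 | 1.9 |
| 10% | 4 to 12 | 1.8 |
| 20% | 8 to 24 | 1.6 |

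**7. What could this do to the comparison?** All four inputs are assumptions, per 100 patient-years: VKA MBE 2.5, of which 0.40 haemorrhagic stroke; dabigatran MBE 2.2, of which 0.12.

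| Haemorrhagic strokes recorded only as stroke | Dabigatran / VKA | Rate ratio | Undercount VKA | Undercount dabigatran |
|---|---|---|---|---|
| None | 2.20 / 2.50 | 0.88 | 0% | 0% |
| Half | (2.2 − 0.06) / (2.5 − 0.20) = 2.14 / 2.30 | 0.93 | 0.20 / 2.5 = 8% | 0.06 / 2.2 = 2.7% |
| All | (2.2 − 0.12) / (2.5 − 0.40) = 2.08 / 2.10 | 0.99 | 0.40 / 2.5 = 16% | 0.12 / 2.2 = 5.5% |

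Life-threatening bleeds are a subset of MBEs, so the same lost events would be at least as large a proportion of that outcome.

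**The case against.** The strongest reply is that the text does not show any event being lost.

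- **Bleeding-page restriction.** A reader might infer that MBE, too, is limited to the bleeding page. The documents do not support this: the wording stands only in the life-threatening bullet, and MBE falls under the general outcome-CRF rule. What stands is that the MBE source is left open.
- **Certainty of loss.** A reader might infer that these strokes are missed. The CRF is not shown, and a separate stroke entry is itself an inference. The protocol lists intracranial bleeding under both bleeding definitions, so a careful site has reason to complete both entries. The supported word is *may*.
- **Fatal bleeds.** A reader might call the rule circular and conclude that fatal bleeds are lost. This needs MBE to be programmed from the non-fatal criteria. The yes/no wording in SAP 5.1 leans the other way.
- **Safeguards.** Protocol 5.2.2.2 puts all SAEs and outcome events on SAE or AE forms, and Protocol 8.2 allows complex cross-form checks. The cleaning query may match by outcome type. A suitable check may exist in a data management plan that is not part of these documents.
- **Consequence.** Haemorrhagic stroke is reported separately, the MBE Cox model depends on event numbers, and no confirmatory testing is planned.

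These replies limit the claim. They do not supply the missing rule: the SAP gives life-threatening bleeds a source that need not contain haemorrhagic strokes, and nothing in it adds them.

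**Conclusion.** The point holds in a limited form. SAP 5.1 does not carry haemorrhagic strokes into life-threatening or major bleeding, although Protocol 5.1.2 defines them as both. One recorded only as a stroke would be left out of the life-threatening bleed analysis. It might also be left out of the MBE rates and Cox model, depending on how MBE is sourced.

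The size cannot be derived from the documents. It is zero if sites always complete both entries. The movement from 0.88 to 0.93 or 0.99 shows direction and range only; every input rate is assumed, and the last value requires that no haemorrhagic stroke is also recorded as a bleed. That the loss would fall more on VKA rests on the RE-LY finding cited in the protocol and on similar recording habits in both groups.

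A reader might extend the concern to the main composite. That is not supported, since these patients enter it through stroke or vascular death. The fatal-bleed gap is conditional on how MBE is derived.

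**What to change.** In SAP 5.1, state how MBE status is determined, and derive life-threatening bleed, and hence MBE, as any of:

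1. a bleeding-page event that meets a protocol criterion for life-threatening bleeding;
2. a stroke outcome classified as haemorrhagic, dated at stroke onset;
3. a bleeding-page event linked to a fatal SAE, whether or not another MBE criterion is met.

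Bleeding-page events that meet only the other MBE criteria remain MBEs as now. Count the first event once per patient. SAP 7.6 already disregards recurrent events for incidence rates, so the union does no harm where sites completed both entries.

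Add a cleaning query for haemorrhagic strokes and fatal haemorrhage SAEs that have no bleeding-page entry. Do not convert SAEs directly into MBEs: that would bypass the outcome-CRF hierarchy in SAP 5.1 and replace the site's assessment with adverse event coding.

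The cost is SAP wording, a few lines of programming and some site queries. Stroke type must already be in the data, since SAP 7.6 plans haemorrhagic stroke rates. Reported bleeding rates may become slightly higher.

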5.3 OTHER VARIABLES

Further variable definitions could be considered for exploratory analyses.

6. GENERAL ANALYSIS DEFINITIONS

6.1 EXPOSURE

Similar treatment regimens (e.g. OAC monotherapy, or in combination with other antithrombotics) will be pooled for analysis by antithrombotic treatment choice at baseline, as specified in [Table 6.1:1](#). The following treatment groups will be used for summary of data (including adverse event data):

Table 6.1: 1 Treatment groups

Treatment group (short name; displayed in column headers)	Treatment group (long name)	Description of treatment regimens included
Dabigatran	(Combinations with) DE -excluding other NOACs, VKA	Patients with DE +/- other antithrombotics excluding patients with DE + {NOAC, VKA}
VKA	(Combinations with) VKA -excluding NOACs:	Patients with VKA +/- other antithrombotics excluding patients with VKA + {NOAC}
Rivaroxaban	(Combinations with) Rivaroxaban -excluding other NOACs, VKA	Patients with Rivaroxaban +/- other antithrombotics excluding patients with Rivaroxaban + {N OAC, VKA}
Apixaban	(Combinations with) Apixaban -excluding other NOACs, VKA	Patients with Apixaban +/- other antithrombotics excluding patients with Apixaban + {NOAC, VKA}
Edoxaban	(Combinations with) Edoxaban -excluding other NOACs, VKA	Patients with Edoxaban +/- other antithrombotics excluding patients with Edoxaban + {NOAC, VKA}
ASA	(Combinations with) ASA - excluding VKA, NOACs:	Patients with ASA +/- other antithrombotics excluding patients with ASA + {NOAC, VKA}
None	None	no treatment
Total*	Total	All patients irrespective of treatment

NOAC := Dabigatran, Rivaroxaban, Apixaban, Edoxaban

OAC := VKA, NOAC

*The total group includes all possible treatments (including those in [Table 6.1:2](#))

Analysis of baseline data will include all treatment groups defined in the table above, analysis of longitudinal outcome event data (incidence rates and cumulative risks only) will be as well performed for these treatment groups for all groups with at least 500 patients at baseline. For further analyses, baseline data on the dabigatran cohort will be analysed stratified by dabigatran mono vs combi- therapy (DE only, DE + other antithrombotics excluding patients with DE + { NOAC, VKA}) and by dabigatran dose group (DE 110mg bid, DE 150mg bid, DE 75mg bid, DE other dose (incl. 220mg QD, 150mg QD, 110mg QD, 75mg QD, other, unknown)) for the categories with at least 100 patients at baseline. Longitudinal data on the dabigatran cohort will be analysed stratified by dabigatran mono vs combi- therapy and by dabigatran dose group (e.g. DE 110mg bid, DE 150mg bid, DE 75mg bid) for the categories with at least 500 patients at baseline.

Administration of 'combinations of oral anticoagulants' (see [table below](#) for definition) are not recommended for long-term use. If after querying, 'combinations of oral anticoagulants' are still confirmed for some patients, they will only be counted for the "Total column" (according to the definitions provided in the [table above](#)) for analysis of baseline data. The following additional treatment groups will be defined but will not be part of the main tables on baseline data.

Table 6.1: 2 Additional treatment groups

Treatment group (short name)	Treatment group (long name)	Description of treatment regimens included
Combinations of oral anticoagulants	Combinations of oral anticoagulants	multiple treatments in {Dabigatran, VKA, Rivaroxaban, Apixaban, Edoxaban} +/- other antithrombotics
Antiplt other than ASA	(Combinations of) Antiplatelets other than ASA	Patients with one or multiple treatments in {Clopidogrel, Ticlopidine, Prasugrel, Dipyridamole, Ticagrelor}

AE data will be tabulated for all treatment groups shown in [Table 6.1:1](#) except the no treatment group.

